6.5 EXPECTEDNESS OF ADVERSE EVENTS

An expected AE is one that is consistent with the known risk information described in the current Investigator's Brochure. An AE is considered unexpected if it is not listed in the Investigator's Brochure or it is not listed at the specificity or severity that has been observed. This will be assessed by the medical monitor or sponsor-investigator upon receipt of the initial AE report.

6.6 ADVERSE EVENTS OF SPECIAL INTEREST

Adverse events of special interest that are particularly specific to this study will be collected, assessed and recorded in the eCRF as an AE. These events of special interest will be collected in addition to the SAEs described in Section 6.1 and include the following clinical situations (see Section 3.3.2):

- Frequency of injection site reactions and systemic reactions among the study participants that are assessed as severe between Day 0 and 7 will be captured as an AE.
- Clinically significant changes in hematology between screening and Week 4 that are assessed as severe will be captured as an AE.

6.7 REPORTING OF SERIOUS ADVERSE EVENTS

Any SAE occurring after the participant has been vaccinated with rBV A/B must be reported to the medical monitor and sponsor-investigator by phone, fax, or e-mail within 24 hours of the time the investigator becomes aware of the SAE ([Table 4](#)). Urgent reporting of SAEs is required for the following reasons:

1. To enable the sponsor-investigator to fulfill the reporting requirements to the appropriate regulatory authority
2. To facilitate the sponsor-investigator's rapid dissemination of information about SAEs to other investigators or sites in a multicenter study
3. To facilitate reporting unanticipated and/or serious problems involving risk to participants to the IRB within 48 hours.

Table 4. Timeline for Reporting Serious Adverse Events to Medical Monitor and Sponsor-Investigator

Initial SAE Report		Follow-up SAE Report	
Time Frame	Documents	Time Frame	Documents
24 hours	SAE report	7 days	Updated SAE report

SAE = serious adverse event.

The SAE report form will be completed as thoroughly as possible, including the following information:

- Participant identification information
- All available details about the event
- Causality of each SAE
- Signature of the investigator

The SAE report will be forwarded to the DSMB within the designated time frames. If the investigator does not have all information about an SAE, the investigator will NOT wait to receive additional information before notifying the DSMB of the SAE and completing the form. The form will be updated when additional information is received.

IND Safety Reports: The investigator will report a suspected adverse reaction that is both “serious” and “unexpected” to FDA in accordance with the timeframe outlined in 21 CFR 312.32. FDA and all participating investigators will be notified of potentially serious risks identified from any source within 15 calendar days after the sponsor-investigator receives the safety information and determines that it is reportable [21 CFR312.32 (c) (1)]. The sponsor-investigator must also notify FDA of any unexpected fatal or life-threatening suspected adverse reaction as soon as possible but in no case later than 7 calendar days after the sponsor-investigator’s initial receipt of the information

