E-mail : [contact]

Medical monitor:

[name] [name]., F.A.C.P.
Clinical Professor, Emeritus
UCB-UCSF Joint Medical Program
Chair, Editorial Board, UC Berkeley *Wellness Letter*
University of California, Berkeley
[name]
[contact]
[contact]
E-mail: [contact]

STUDY SYNOPSIS

Name of sponsor company: California Department of Public Health (CDPH)	
Name of investigational product: Recombinant Botulinum Vaccine A/B (rBV A/B)	
Names of active ingredients: Recombinant Botulinum Antigen A and Antigen B adsorbed to 0.2% (wt/vol) Alhydrogel™	
Title of study: Tolerability and Immunogenicity of a Single 40- μ g Dose of Recombinant Botulinum Vaccine A/B (rBV A/B) for the Production of BabyBIG® in Volunteers with Existing Botulinum Immunity	
Sponsor Investigator: [name]	
Number of sites: 2	
Study period: 18 months	Phase of development: Phase 2
Objectives:	
Immunogenicity: The immunogenicity objective of this study is to evaluate the effects of a single 40- μ g dose of the recombinant botulinum vaccine A/B (rBV A/B) on botulinum toxin type A and type B neutralizing antibody concentration (NAC) over a 12-week period following vaccination in participants who have previously been immunized with pentavalent botulinum toxoid (or pentavalent botulinum toxoid and rBV A/B) for occupational protection.	
Safety: The safety objective of this study is to obtain safety information during the 12-week study period and at 6 months post-vaccination on the use of rBV A/B in a population of participants previously immunized with pentavalent botulinum toxoid (or pentavalent botulinum toxoid and rBV A/B) for occupational protection.	
Exploratory: The exploratory objective of this study is to collect source plasma from participants that contains neutralizing antibodies against botulinum toxin type A and type B for the production of BabyBIG .	
Methodology: This Phase 2, open-label, uncontrolled study designed to evaluate safety, tolerability, and immunogenicity of a single dose of rBV A/B in healthy participants previously immunized with pentavalent botulinum toxoid (or pentavalent botulinum toxoid and rBV A/B) for occupational protection will be conducted to collect source plasma for potential use in the production of BabyBIG and to evaluate safety and immunogenicity of the vaccine in these participants over a 12-week period, with a follow-up safety assessment at 6 months.	

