4.4.2 Study Stopping Rules

For this study, the following are the dose stopping rules; and, if they occur, all dosing will stop, the DSMB (Section 6.10) will convene, review the data collected, and make a recommendation for continued dosing.

- If any participant has an SAE (see Section 6.1 for a definition) considered possibly, probably, or definitely related to the vaccine
- Two or more participants with a Grade 3 (severe) or higher similar hematologic abnormality, considered possibly, probably or definitely related to the vaccine
- Two or more participants with neuromuscular AEs considered possibly, probably or definitely related to the vaccine

If the DSMB determines that an SAE was a vaccine-related SAE, then the sponsor-investigator will provide the DSMB's recommendation along with the SAE report to the FDA and seek the Agency's guidance on resuming the study.

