6.10 DATA AND SAFETY MONITORING BOARD

The DSMB will meet quarterly throughout the study and as needed as described in Section 4.4. The specific information that will be reviewed to make its recommendation will be safety data and neutralizing antibody concentrations.

In addition, the DSMB will convene at any time during the study if a stopping rule is met (see Section 4.4.2)

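### Two of the three study stopping rules count non-serious events that the protocol does not reliably collect, report within a set time, or tally across its two sites

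*Protocol*

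**What the plan says.** Protocol 4.4.2 lists three conditions under which all dosing stops and the DSMB convenes. The first is any SAE considered at least possibly related. The second is "Two or more participants with a Grade 3 (severe) or higher similar hematologic abnormality, considered possibly, probably or definitely related to the vaccine". The third is "Two or more participants with neuromuscular AEs considered possibly, probably or definitely related to the vaccine"; it names no grade.

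The provisions for getting information to the people who would act are these:

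- **Protocol 6.7 and Table 4.** "Any SAE occurring after the participant has been vaccinated with rBV A/B must be reported to the medical monitor and sponsor-investigator", and this must happen "within 24 hours of the time the investigator becomes aware of the SAE". The report then goes to the DSMB. Only SAEs are covered.
- **Protocol 6.6.** Severe injection site and systemic reactions on Days 0 to 7, and severe clinically significant hematology changes up to Week 4, "will be collected, assessed and recorded in the eCRF as an AE". No deadline or recipient is given.
- **Protocol Table 1, footnote r (repeated in the SAP).** Querying and collection are limited to SAEs and new onset chronic illnesses.
- **Protocol 8.1.** The study/data monitor must review and source-verify all eCRFs. The medical monitor may look at them.
- **Protocol 6.10.** "The DSMB will meet quarterly throughout the study and as needed as described in Section 4.4". It adds that the board convenes at any time if a stopping rule is met. SAP 3.6 repeats the quarterly schedule and leaves the DSMB displays to be settled elsewhere.

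The synopsis gives "Number of sites: 2" and up to 50 participants.

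**The concern.** A stopping rule works only if someone is bound to learn that it has been met. Rules 2 and 3 are study-wide counts, and they matter only for events that are not serious. The protocol itself warns in 6.3 that severe and serious are different things. Yet the timed reporting route is written for serious events alone.

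If each site has one qualifying case, the rule is met while each investigator sees a single case. Section 6.7 gives rapid sharing of information with other sites as a reason for urgent reporting, so the need is recognised, but only for SAEs. What is at stake is continued vaccination after the study's own stopping condition has been satisfied.

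**Working it through.** The documents give no figure on this point, so there is nothing to reproduce. The check is mainly a comparison of sections; the arithmetic is illustration.

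**Step 1: what rules 2 and 3 add.** If any qualifying hematologic or neuromuscular event is serious and related, rule 1 already stops dosing. Rules 2 and 3 therefore change the outcome only when all the qualifying events are non-serious.

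**Step 2: follow such an event through the plan.**

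- *Non-serious Grade 3 or higher hematology result.* It is detected at the Week 4 draw, the only scheduled post-dose study hematology panel, so it may be up to about four weeks old. It is then entered in the eCRF under 6.6, untimed. The 24-hour route does not apply.
- *Severe neuromuscular AE, Days 0 to 7.* It can enter the eCRF as a severe systemic reaction under 6.6, untimed.
- *Mild or moderate neuromuscular AE.* It counts under rule 3, but 6.6 covers severe events only and footnote r limits collection to SAEs and new onset chronic illnesses. Section 6.1 puts complaints in source documents and directs only SAE information to the eCRF. The Week 4 and 10 calls (5.2.2.5) ask more widely but direct only serious items to the eCRF. Section 6.9 says the diary collects muscle weakness and neuromuscular events; the Appendix C form lists neither.

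**Step 3: who counts.** None of 4.4.2, 6.6, 6.7, 6.10 or 8.1 gives a role the task of adding cases across sites.

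**Step 4: illustration.** Accrual pattern, site split and event rate are all assumptions.

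- Dosed per quarter = 50 × 3 / (accrual months): 50 × 3/18 = 8.3; 50 × 3/12 = 12.5; 50 × 3/6 = 25. These are maxima, for a second case just after a meeting. If its timing were uniform between meetings, the averages would be half: about 4, 6 and 12.5.
- Chance that exactly two cases fall at different sites = n1 × n2 / C(50,2), with C(50,2) = 1225: 25 × 25/1225 = 51%; 35 × 15/1225 = 43%; 40 × 10/1225 = 33%.
- For a per-participant qualifying rate p, P(rule met) = 1 − (1−p)^50 − 50p(1−p)^49. P(met by exactly one case at each site) = n1·p(1−p)^(n1−1) × n2·p(1−p)^(n2−1). For p = 2% and 25/25, the latter is (25 × 0.02 × 0.98^24)² = 0.308² = 9.5%.

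| p | Rule met | One case per site, 25/25 | One case per site, 40/10 |
|---|---|---|---|
| 1% | 8.9% | 3.9% | 2.5% |
| 2% | 26.4% | 9.5% | 6.1% |
| 5% | 72.1% | 13.3% | 8.5% |
| 10% | 96.6% | 4.0% | 2.5% |

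The split case becomes rarer at high rates because, with three or more cases and two sites, one site must see two itself.

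**The case against.** A reader might infer that these events have no route at all, that they must wait for a quarterly meeting, and that about 12 more people would be vaccinated meanwhile. The documents do not support that reading.

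- Appendix E tells participants to seek care at once and notify round-the-clock contacts about listed neuromuscular symptoms, and about severe or life-threatening ones. The contacts' roles were removed from the public text, so it cannot be claimed that nobody central hears of such events. Rule 3 is less exposed for that reason.
- Section 8.1 requires review of every eCRF by the study/data monitor, so central review is not merely optional.
- Section 6.5 refers to an initial AE report reaching the medical monitor or sponsor-investigator, which suggests that some AE reports do go there.
- Section 6.10 lets the DSMB convene at any time, and 4.4.2 makes the stop automatic. No quarterly wait is built in.
- The figure of 12 is a maximum under one assumed accrual pattern. If accrual were fast, much dosing would come before any Week 4 result, and quicker reporting would help less.

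All of this stands and narrows the point. It does not remove it. Appendix E asks the participant to call as soon as possible, but no section requires the contacts to relay or pool what they hear, and a laboratory abnormality without symptoms prompts no call. The eCRF review has no timetable and no counting duty. Section 6.5 creates no reporting duty or deadline for non-serious AEs. Section 6.10 gives the power to meet but no means of learning that a rule has been met. For mild or moderate neuromuscular AEs the quarterly meeting is not even a backstop, because they may never enter the eCRF.

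**Conclusion.** The gap is real and lies in detection, not in the thresholds or in the authority to stop. Followed as written, the collection and reporting sections leave out events on which rules 2 and 3 depend, so dosing could continue after a rule has been met. The hematology rule is the most exposed: it has no symptom-driven telephone route, its scheduled post-dose test is at Week 4, and its eCRF entry is untimed.

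The conclusion rests on the text alone. The numbers only indicate scale: at most about 8, 12 or 25 participants dosed before the next quarterly meeting for even accrual over 18, 12 or 6 months, and a 33% to 51% chance that two cases fall at different sites for splits from 40/10 to 25/25. The documents state no accrual pattern, site split or event rate. Nor do they show that cases would in fact be missed; informal contact between sites, or the safeguards above, may catch them. The change is worth making because the stop is meant to protect participants and the remedy is cheap.

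**What to change.** Reconcile Protocol 4.4.2, 6.6, 6.7, Table 4, 6.10 and footnote r of Table 1 (with the matching SAP footnote) so that:

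1. every event counted by a 4.4.2 rule is collected, whatever its grade where the rule states none;
2. each such event is reported to the medical monitor and sponsor-investigator on the 24-hour route that already exists for SAEs;
3. a named existing role keeps the tally across both sites and gives notice when a rule is met.

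The thresholds and the automatic stop in 4.4.2 are not changed, and nothing here alters who decides on dosing. The cost is a few sentences across those sections and a few extra 24-hour reports. It needs no new visits, tests or staff.

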6.8 FOLLOW-UP OF SERIOUS ADVERSE EVENTS

All SAEs (as well as clinically significant changes in hematology that result in a severe or serious adverse event) will be followed until the occurrence of one of the following:

- The event resolves.
- The condition stabilizes.
- The event is otherwise explained.
- The participant is lost to follow-up.

The appropriate SAE report form will be updated for SAEs only once the SAE resolves, stabilizes, is otherwise explained, or the participant is lost to follow-up. The investigator will also ensure that additional updates include any supplemental data that may explain causality of the event(s).

New or updated information will be recorded on a copy of the initially completed SAE report, with all the changes signed and dated by the investigator or designee. The updated SAE report will then be signed by the investigator and resubmitted to the DSMB as outlined in [Table 4](#).

6.9 INJECTION SITE AND SYSTEMIC REACTIONS

Commonly seen injection site reactions for rBV A/B are consistent with reactions in participants vaccinated with other recombinant protein vaccines that include Alhydrogel™. The majority of reactions at the injection site seen to date with rBV A/B have been mild or moderate in severity and included erythema, pain, pruritus, and swelling. Participants will be actively monitored for localized and systemic reactions to the injections and an anaphylaxis (epinephrine) kit will be available at the time of injections.

The definitions to be used to determine severity of injection site reactions are provided in [Table 5](#).

Table 5. Protocol Definitions for Severity of Injection Site, ie., Local Reactions

Local Reaction to Injectable Product	Mild (Grade 1)	Moderate (Grade 2)	Severe (Grade 3)	Potentially Life-Threatening (Grade 4)
Injection site pain	Does not interfere with activity	Repeated use of nonnarcotic pain reliever >24 hours or interferes with activity	Any use of narcotic pain reliever or prevents daily activity	ER visit or hospitalization
Injection site tenderness	Mild discomfort to touch	Discomfort with movement	Significant discomfort at rest	ER visit or hospitalization
Injection site erythema (redness) ^a	2.5-5.0 cm	5.1-10.0 cm	>10.0 cm	Bullae, necrosis, or exfoliative dermatitis
Injection site swelling (induration) ^b	2.5-5.0 cm and does not interfere with activity	5.1-10.0 cm or interferes with activity	>10.0 cm or prevents daily activity	Necrosis

ER = emergency room.

^a In addition to grading the measured local reaction at the greatest single diameter, the measurement should be recorded as a continuous variable.

^b Induration (swelling) should be evaluated and graded using the functional scale as well as the actual measurement.

Systemic reactions collected in the diary are severity of muscle weakness, malaise, rash, headache, nausea, chest discomfort, breathing difficulties, anxiety, feelings of depression, and neuromuscular TEAEs. For systemic reactions, use the guidance provided in Appendix B.

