Safety considerations: Participants will be monitored for serious adverse events after vaccination throughout the 12-week study period and at the Week 26 phone call follow-up. Administration site reactions and systemic reactions will be monitored with a diary provided to collect information, including diameter of any swelling and redness around the injection site and any generalized symptoms between Week 0 and Week 1 in order to determine if any severe reactions or serious adverse events occurred during this 1-week period post-vaccination. All severe local and systemic reactions will be recorded in the electronic case report form (eCRF). Hematology, serum chemistry, and urinalysis specimens will be collected at screening, and repeat hematology at Week 4 for monitoring of any clinically significant changes that result in a severe or serious AE. Clinically significant changes in hematology that result in a severe or serious AE will be recorded on the eCRF. Female participants of childbearing potential will have a urine pregnancy test at screening and again at Week 0 prior to receipt of the vaccine. Source plasma collection will occur for eligible donors at licensed collection locations. If the participant fails to meet donor criteria at any time during the plasmapheresis period, the participant will continue to be followed for serious adverse events according to the study schedule. Participants will be contacted by phone at Weeks 1, 4, and 10. At Week 26, participants will be queried for occurrence of serious adverse events and serious new onset chronic illnesses (NOCIs), which will be recorded by the investigator (or designee) on serious adverse events recording sheets and entered in the eCRF. Vital signs will be monitored at screening, Week 0 (vaccine visit), and at each plasma collection visit.

STUDY SYNOPSIS (continued)

Name of sponsor company: California Department of Public Health (CDPH)
Name of investigational product: Recombinant Botulinum Vaccine A/B (rBV A/B)
Names of active ingredients: Recombinant Botulinum Antigen A and Antigen B adsorbed to 0.2% (wt/vol) Alhydrogel™
Statistical methods: The data will be summarized in tables listing the mean, standard deviation or standard error, median, minimum, maximum, and number of participants for continuous data, or in tables listing count and percentage for categorical data, where appropriate.

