3.3.2 Safety

Primary safety endpoints will be collected over a 12-week period and will be as follows:

- Frequency of injection site reactions and systemic reactions that are characterized as severe during the 0-7 day diary collection period.
- Frequency of injection site reactions and systemic reactions that are characterized as serious adverse events (SAEs) [Definitions for local injection site reactions are in Section 6.9 and systemic reactions are located in Appendix B. Definition of SAE is located in Section 6.1]
- Participant incidence of treatment-related serious adverse events (Adverse event toxicity tables are located in [Appendix B](#))
- Participant incidence of serious NOCIs
- Clinically significant changes from baseline health resulting in serious adverse events
- Clinically significant changes in hematology between screening and Week 4 resulting in severe or serious adverse events

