Diary review			X					
Serious adverse event collection ^r		X	X	X	X		X	X
Concomitant medication information	X ^t		X ^s	X ^s	X ^s		X ^s	X ^s
Phone call			X	X	X			X

HBV = hepatitis B virus; HCV = hepatitis C virus; HIV = human immunodeficiency virus; NAC = neutralizing antibody concentration; rBV A/B = recombinant botulinum vaccine A/B.

a. Week 1, Week 4, and Week 10 Follow-up Calls must occur with ± 3 days of the scheduled time.

b. Final Study Visit will be an on-site visit at Week 4 for participants who opt not to participate or who have been determined to be ineligible for donation for the entire study. All final assessments occurring at Week 12 will occur at Week 4 for these participants.

c. Extension of plasmapheresis for up to 14 weeks is optional

- d. Final on-site Study Visit must occur within \pm 7 days of the scheduled time.
- e. Final follow-up call for safety must occur within \pm 1 week of the scheduled time.
- f. Plasmapheresis-specific informed consent formed will be signed at the source plasma center.
- g. Physical examination will be performed as part of source plasma donor screening at the plasma collection center
- h. Female participants of childbearing potential must have a negative pregnancy test within 24 hours prior to vaccination.
- i. Participants will have vital signs taken twice at Visit 1: prior to injection, and 30 minutes (\pm 5 minutes) after receiving the injection.
- j. HIV, HBV, and HCV tests will be performed on each donated source plasma unit
- k. Results from screening tests must be available before Vaccination Visit
- l. Study participants will go to central lab or plasma center for this draw (not an on-site visit).
- m. Baseline NAC sample must be collected before rBV A/B injection and before plasmapheresis
- n. Participants not donating plasma must go to site for NAC collection within \pm 3 days of the scheduled time.
- o. May occur up to twice a week for up to 14 weeks (if hemoglobin and total protein remain within acceptable range) following vaccination with rBV A/B.
- p. At this visit, participants will be monitored for at least 30 minutes after injection for a possible reaction.
- q. In the diaries, participants record adverse events in order to determine SAE, oral temperature and injection site information.
- r. Only serious adverse events and new onset chronic illnesses are to be queried for and collected

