APPENDIX C
PARTICIPANT DIARY

**Tolerability and Immunogenicity of a Single 40- μ g Dose of Recombinant
Botulinum Vaccine A/B (rBV A/B) for the Production of BabyBIG® in
Volunteers with Existing Botulinum Immunity**

Reaction Recording Sheet – Participant Home Diary

Study Site/Location*: _____ / _____

Participant Study ID Number*: _____

Participant Name: _____

Recombinant vaccine given: Date: _____ / _____ / _____ Time: _____ AM / PM

	1 day 24 hrs	2 days 48 hrs	3 days 72 hrs	4 days 96 hrs	5 days 120 hrs	6 days 144 hrs	7 days 168 hrs
Local reactions:							
Soreness?	Y	N	Y	N	Y	N	Y
Itching?	Y	N	Y	N	Y	N	Y
Erythema? (mm) ^a							
Induration? (mm) ^a							
Systemic reactions:							
General malaise?	Y	N	Y	N	Y	N	Y
Fatigue?	Y	N	Y	N	Y	N	Y
Lethargy?	Y	N	Y	N	Y	N	Y
Chills, fever?	Y	N	Y	N	Y	N	Y
Lumps, soreness? (not local)	Y	N	Y	N	Y	N	Y
Stiff back, stiff neck?	Y	N	Y	N	Y	N	Y
Nausea, vomiting, or diarrhea?	Y	N	Y	N	Y	N	Y
Other GI symptoms?	Y	N	Y	N	Y	N	Y
Itching, hives?	Y	N	Y	N	Y	N	Y

^a Please use tool provided to measure. Please list any medications used to treat the potential reactions above:

If you answered **yes** to any of the above potential reactions, please record additional comments i.e., date/time of reaction, symptoms

If additional space required, please continue on back of this form.

* To be filled in by study staff

Ver. August 2018

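### The Appendix C diary does not collect all the symptoms, severity and temperature that the protocol says it does, and its one review may precede Day 7, so some severe Day 0–7 reactions may be missed or mis-graded

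*Protocol*

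**What the plan says.** The endpoint comes first in Protocol Section 3.3.2: "Frequency of injection site reactions and systemic reactions that are characterized as severe during the 0-7 day diary collection period". The synopsis (Safety considerations) gives the diary the task of collecting, besides swelling and redness, "any generalized symptoms between Week 0 and Week 1 in order to determine if any severe reactions or serious adverse events occurred".

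On content, Section 6.9 states of systemic symptoms that those "collected in the diary are severity of muscle weakness, malaise, rash, headache, nausea, chest discomfort, breathing difficulties, anxiety, feelings of depression, and neuromuscular TEAEs". Table 1 footnote q, repeated in the SAP schedule, states: "In the diaries, participants record adverse events in order to determine SAE, oral temperature and injection site information".

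On grading, Section 3.3.2 says: "Definitions for local injection site reactions are in Section 6.9 and systemic reactions are located in Appendix B". Section 6.9 repeats: "For systemic reactions, use the guidance provided in Appendix B". Table 5 note b adds: "Induration (swelling) should be evaluated and graded using the functional scale as well as the actual measurement".

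The form itself (Appendix C) has seven daily columns. Its nine systemic rows and the local soreness and itching rows are Yes/No. Erythema and induration are in mm. There is a line for medications, and a participant who answers yes is told: "please record additional comments i.e., date/time of reaction, symptoms".

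A second form, Appendix E, is given out at the same visit. It has free-text event rows, start and end times, treatment, a participant-rated severity (mild, moderate, severe) and a list of neuromuscular warning symptoms.

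On timing, Table 1 marks diary review only at the Week 1 call, which footnote a allows three days either way.

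**The concern.** The form that feeds the first-listed primary safety endpoint does not match the text describing it. An endpoint that counts only severe reactions depends on two things: that the reaction is brought up, and that what is known about it is enough to assign Grade 3. Gaps in the prompts threaten the first. A missing temperature and missing functional entries threaten the second.

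The timing adds to this. Protocol Section 8.2.5 analyses the severe reactions gathered at the Week 1 call, and Section 5.2.2.3 makes the staff notes from that call the source document. If the call comes early, the last diary days have no scheduled review. SAP Section 8.5 plans no separate summary or listing of diary data, so a reader of the report could not see the gap.

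**Working it through.** There is no stated figure to reproduce. The check sets the text beside the forms, then does the calendar arithmetic.

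**1. Symptoms.** The ten terms of Section 6.9 against the two forms:

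| Section 6.9 term | Row in Appendix C | Named in Appendix E |
|---|---|---|
| Malaise | yes | – |
| Nausea | yes (with vomiting and diarrhea) | – |
| Rash | in part (itching/hives row) | – |
| Muscle weakness | no | in part (limb weakness) |
| Breathing difficulties | no | in part (shallow breathing) |
| Neuromuscular events | no | yes (symptom list) |
| Headache | no | no |
| Chest discomfort | no | no |
| Anxiety | no | no |
| Depression | no | no |

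Appendix C: 2 present + 1 partial + 7 absent = 10. Of the 7 absent, Appendix E names 3 at least in part, so 7 − 3 = 4 are prompted on neither form.

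**2. Severity.** Appendix C asks severity for none of its 9 systemic rows. Its comments line asks for timing and symptoms, not severity or function. For induration it takes the size but not the functional grade that Table 5 note b requires. Appendix E does ask severity, but on a three-level participant scale, whereas Table 5 and Appendix B use four grades with their own criteria.

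**3. Temperature.** Appendix B Table 6 puts Grade 3 fever at 39.0–40.0 °C. Appendix C has a chills/fever row answered Yes/No, and Appendix E has no temperature field. Day 0 vital signs end 30 minutes after injection, and plasma donation visits, which do measure temperature, start no earlier than one week after vaccination. Neither fills the diary week.

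**4. Timing.** Week 1 call = Day 7 ± 3 = Days 4 to 10, which is 7 permitted days, 3 of them before Day 7. Assuming the entry due on the day of the call has been made, the unreviewed entries are:

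- Day 4 call: 7 − 4 = 3 of 7 (43%)
- Day 5 call: 7 − 5 = 2 of 7 (29%)
- Day 6 call: 7 − 6 = 1 of 7 (14%)

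The next scheduled study safety contact is Week 4 = Day 28 ± 3 = Days 25 to 31. For a reaction on Days 5 to 7 that is 25 − 7 = 18 to 31 − 5 = 26 days later, unless the participant reports it sooner.

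**5. Scale of one missed event.** Exact (Clopper–Pearson) 95% intervals are assumed, because the documents name no method. Lower limit = Beta(0.025; x, n − x + 1), or 0 when x = 0; upper limit = Beta(0.975; x + 1, n − x).

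| n | One severe reaction recorded | The same reaction missed |
|---|---|---|
| 50 (planned maximum) | 1/50 = 2.0% (0.05–10.6%) | 0/50 = 0% (0–7.1%) |
| 30 (assumed) | 1/30 = 3.3% (0.1–17.2%) | 0/30 = 0% (0–11.6%) |

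These figures show what one missed event would do to the report. They do not show that one is likely.

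**The case against.** **Appendix E may count as part of the diary.** Footnote q speaks of diaries in the plural and says adverse events are recorded in them; Appendix E has the event rows. SAP Section 8.5 describes a home diary that also runs through the study period to capture adverse events. On that reading severity is collected. This stands: a reader might infer that the study collects no severity for first-week reactions, and the documents do not support that. What is left is the difference in scale, the missing temperature and the four unprompted terms.

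**The call is meant to follow a complete diary.** The synopsis (Experimental procedures) has participants complete a seven-day diary for the Week 1 call, and the ± 3 days is a window shared by three calls. The intent is clear, and the percentages above are calendar worst cases. A reader might infer that up to 43% of diary information would be lost; the documents give no distribution of call days, so no expected loss follows. But the window permits Days 4 to 6, and no later contact requires review of the completed diary.

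**Severe reactions have other routes to the record.** Appendix E tells participants with severe symptoms to seek care and notify the study at once, and it is queried again at Weeks 4, 10 and 26. Table 1 footnote s asks about medication for severe first-week reactions. Donors are asked about reactions at Weeks 4 and 10. Protocol Section 6.6 and SAP Section 8.1 take in severe Day 0–7 reactions without tying them to one contact. These routes reduce the risk. They do not remove it: Section 5.2.2.5 sends only serious reactions from the donor calls to the eCRF, and the non-donor Week 4 visit (Section 5.2.2.4) lists no review of non-serious systemic reactions.

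**Staff grade, not participants.** Protocol Section 6.3 rests severity on the investigator's judgment, and a Yes can prompt further questions. This largely answers the functional criteria, which a participant can describe by phone. It does not answer fever, unless the participant happened to take and remember a temperature, or symptoms about which neither form asks.

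**Conclusion.** The mismatch is real and can be checked on the page. Appendix C lacks rows for seven of the ten terms it is said to cover, has no systemic severity entry and has no temperature. With Appendix E counted in full, neither form records a temperature or prompts for headache, chest discomfort, anxiety or depression, and the only scheduled diary review may come before Day 7. Some severe Day 0–7 reactions may therefore be missed or mis-graded.

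The size cannot be estimated from the documents. A reader might infer that the severe-reaction rate will be understated; that goes too far, because later contacts, immediate reporting and staff questioning may recover the events. The endpoint is descriptive, has no success threshold, and its count is not a stopping rule in Section 4.4.2. The effect is on the completeness of the safety report.

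This rests on two assumptions: that the row labels of Appendix C, whose Y/N columns are broken in the text as read, are complete, and that each diary column is filled in on its own day. The change is worth making because the protocol already states what the diary should collect.

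**What to change.** Revise Appendix C to add:

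- the missing Section 6.9 terms, including a proper rash item
- a daily oral temperature
- a severity or functional entry for each symptom, mapped to Table 5 and Appendix B, including the functional item for induration

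Hold the Week 1 diary review only after the Day 7 entry is complete, for example on Days 8–10, or repeat it when the call was made earlier. With a Day 8–10 review, none of the seven entries is still outstanding, against up to three now.

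The cost is a form that takes slightly longer to fill in, and a narrower call window or a second short call for early callers. No visit is added.
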